9.7.1.1 Definition for TEAEs of Fat-Soluble Vitamin Deficiency, Diarrhoea, and Hepatotoxicity

The following TEAEs have been defined based on the population under study:

- New or worsening of fat-soluble vitamin deficiency refractory to clinically recommended vitamin supplementation.

All Investigator-reported verbatim terms related to decreases in vitamin levels or vitamin deficiency (e.g., preferred term of hypovitaminosis, Vitamin A decreased, Vitamin A deficiency) with the relevant concomitant medication records reviewed by the Medical Monitor, queried as needed, and the appropriate MedDRA preferred terms reported.

- Clinically significant diarrhoea, defined as any of the following:
 - Diarrhoea that persists for 21 or more days without any other aetiology based on medical review of other concurrent AEs for possible other causes of the diarrhoea or diagnostic testing (e.g., viral infections)

- Reported by the Investigator as severe in intensity or reported as an SAE due to the requirement for hospitalisation or as an important medical event
- Diarrhoea with concurrent dehydration requiring treatment with oral or intravenous rehydration and/or other treatment intervention based on medical review of AEs and concomitant medications
- Hepatotoxicity: based on the SMQ of *Drug Related Hepatic Disorders*—comprehensive search SMQ (narrow and broad)
- Possible Sequelae of FSV Deficiency: based on the Specified TEAEs with PTs are listed in [Appendix G](#).

For each of these categories, tabular summaries will be presented by MedDRA SOC and PT; the tables will also include the overall incidence of these AEs. Listings of patients with each of the events as defined will be provided.

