9.7.1 Adverse Events

All AEs will be classified by Primary SOC and PT according to MedDRA, Version 26.0 or higher.

AEs will be classified as TEAEs and defined as follows:

A TEAE is an AE occurring during the treatment period and within 28 days follow-up after the last dose that a) Has a start date on or after the first dose date of study drug, or b) Has a start date before the date of the first dose date of study drug, but worsened in severity on or after the date of the first dose date of study drug. If an AE started in Study A4250-005 and was ongoing at the time of enrolment in Study A4250-008, the AE will not be considered a TEAE unless it worsens in severity on or after the date of the first dose date of study drug.

AEs with missing start dates, but with stop dates that either overlap with the treatment period or are missing, will be considered TEAEs. A TEAE with missing drug relationship- will be considered as related. A TEAE with missing severity will be

considered as severe. Details for imputing missing or partial start dates of AEs are described in [Appendix D](#).

For counting of the number of AEs, if 2 AE records have the same preferred term and the start date of the 2nd AE is the same as or next day after the end date of the 1st AE, then they will be counted as one AE only.

An overall summary of the incidence of TEAEs (number of patients with any events and number of events, if applicable) will include the following:

- All TEAEs
- Drug-related TEAEs (AE will be defined as drug-related if causality is either probably, possibly, or definitely related)
- Severe TEAEs
- TEAEs leading to study discontinuation
- Serious TEAEs
- Drug-related serious TEAEs
- TEAEs leading to death
- Any hepatic TEAEs
 - a. Any liver-related TEAE (events that, per the Investigator, are considered related to PFIC)
 - b. Any suspected drug-induced liver injury (DILI) TEAEs (as adjudicated by the Data Safety Monitoring Board [DSMB] and defined in [Section 9.7.1.2](#))
 - c. Any TEAE of liver decompensation (as defined in Section 9.7.1.2)
 - d. Drug related hepatic disorders – comprehensive search SMQ (narrow and broad)
- Any Fat-Soluble Vitamin Deficiency TEAEs refractory to clinically recommended vitamin supplementation (as defined in [Section 9.7.1.1](#))
- Any Possible Sequelae of FSV Deficiency TEAEs by SOC and PT (Specified TEAEs with PTs are listed in [Appendix G](#))

- Any Clinically Significant Diarrhoea TEAEs (as defined in [Section 9.7.1.1](#))

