Appendix G: PT Term of Possible Sequelae of FSV Deficiency

PT Term	Code
Acetabulum fracture	10000397
Activated partial thromboplastin time abnormal	10000631
Activated partial thromboplastin time prolonged	10000636
Adrenal haemorrhage	10001361
Alopecia	10001760
Anastomotic ulcer haemorrhage	10002244
Ankle fracture	10002544
Aortic aneurysm rupture	10002886
Areflexia	10003084
Arrhythmia	10003119
Arterial rupture	10003173
Auricular haematoma	10003797
Bleeding varicose vein	10005144
Blindness	10005169
Blindness transient	10005184
Blood blister	10005372
Blood calcium decreased	10005395
Blood urine	10005863
Bone pain	10006002
Brain stem haemorrhage	10006145
Breast haemorrhage	10006254
Broad ligament haematoma	10006375
Calcium deficiency	10006956
Cephalhaematoma	10008014
Cerebellar haemorrhage	10008030
Cerebral aneurysm ruptured syphilitic	10008076
Cerebral arteriovenous malformation haemorrhagic	10008086
Cerebral haemorrhage	10008111
Cerebral haemorrhage neonatal	10008112
Choroidal haemorrhage	10008786
Clavicle fracture	10009245
Closed fracture manipulation	10009506
Coagulation factor IX level decreased	10009746
Coagulation factor VII level decreased	10009761
Coagulation factor X level decreased	10009775
Coagulation time prolonged	10009799

PT Term	Code
Coagulopathy	10009802
Colonic haematoma	10009996
Complicated fracture	10010149
Compression fracture	10010214
Congenital anomaly	10010356
Conjunctival haemorrhage	10010719
Corneal scar	10011044
Cystitis haemorrhagic	10011793
Decreased immune responsiveness	10011968
Dementia	10012267
Dental caries	10012318
Diarrhoea haemorrhagic	10012741
Disseminated intravascular coagulation	10013442
Diverticulitis intestinal haemorrhagic	10013541
Diverticulum intestinal haemorrhagic	10013560
Dry eye	10013774
Duodenal ulcer haemorrhage	10013839
Duodenitis haemorrhagic	10013865
Dwarfism	10013883
Dysarthria	10013887
Dysphagia	10013950
Ear haemorrhage	10014009
Eccymosis	10014080
Encephalitis haemorrhagic	10014589
Enterocolitis haemorrhagic	10014896
Epistaxis	10015090
Exsanguination	10015719
External fixation of fracture	10015741
Extradural haematoma	10015769
Extravasation blood	10015867
Eye haemorrhage	10015926
Factor IX deficiency	10016077
Femoral neck fracture	10016450
Femur fracture	10016454
Fibula fracture	10016667
Foetal-maternal haemorrhage	10016871
Foot fracture	10016970
Forearm fracture	10016997

PT Term	Code
Fracture	10017076
Fracture delayed union	10017081
Fracture malunion	10017085
Fracture nonunion	10017088

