Optic disc haemorrhage	10030919
Optic nerve sheath haemorrhage	10030941
Orbital haemorrhage	10031045
Osteomalacia	10031250
Osteoporosis	10031282
Osteoporotic fracture	10031290
Ovarian haematoma	10033263
Pancreatic haemorrhage	10033625
Pancreatitis haemorrhagic	10033650
Pathological fracture	10034156
Pelvic haematoma obstetric	10034248
Penile haemorrhage	10034305
Peptic ulcer haemorrhage	10034344
Pericardial haemorrhage	10034476
Perineal haematoma	10034520
Periorbital haematoma	10034544
Petechiae	10034754
Pharyngeal haemorrhage	10034827
Placenta praevia haemorrhage	10035121
Post abortion haemorrhage	10036246
Post-traumatic osteoporosis	10036315
Postpartum haemorrhage	10036417
Premature separation of placenta	10036608
Proctitis haemorrhagic	10036778
Prostatic haemorrhage	10036960
Prothrombin level abnormal	10037048
Prothrombin level decreased	10037050
Prothrombin time abnormal	10037057
Prothrombin time prolonged	10037063

PT Term	Code
Pulmonary alveolar haemorrhage	10037313
Pulmonary contusion	10037370
Pulmonary haemorrhage	10037394
Purpura	10037549
Purpura fulminans	10037556
Purpura neonatal	10037557
Purpura senile	10037560
Radius fracture	10037802
Rectal haemorrhage	10038063
Rectal ulcer haemorrhage	10038081
Renal haematoma	10038459
Renal haemorrhage	10038460
Respiratory tract haemorrhage	10038727
Respiratory tract haemorrhage neonatal	10038728
Retinal haemorrhage	10038867
Retroperitoneal haemorrhage	10038980
Rib fracture	10039117
Ruptured cerebral aneurysm	10039330
Scrotal haematoma	10039749
Senile osteoporosis	10039984
Short stature	10040600
Spinal compression fracture	10041541
Spinal fracture	10041569
Splenic haematoma	10041646
Splenic haemorrhage	10041647
Splinter haemorrhages	10041663
Sternal fracture	10042015
Stomatitis haemorrhagic	10042132
Stress fracture	10042212
Subarachnoid haemorrhage	10042316
Subarachnoid haemorrhage neonatal	10042317
Subcutaneous haematoma	10042345
Subdural haematoma	10042361
Subdural haematoma evacuation	10042363
Subdural haemorrhage	10042364
Subdural haemorrhage neonatal	10042365
Third stage postpartum haemorrhage	10043449
Thrombocytopenic purpura	10043561

PT Term	Code
Thrombotic thrombocytopenic purpura	10043648
Tibia fracture	10043827
Tongue haematoma	10043959
Tooth injury	10044043
Tooth malformation	10044046
Traumatic haematoma	10044522
Tremor	10044565
Ulna fracture	10045375
Umbilical haemorrhage	10045455
Upper gastrointestinal haemorrhage	10046274
Urinary bladder haemorrhage	10046528
Uterine haemorrhage	10046788

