Vascular pseudoaneurysm ruptured	10053949
Epiphyseal fracture	10053962
Implant site haemorrhage	10053995
Vessel puncture site haemorrhage	10054092
Haemorrhagic tumour necrosis	10054096
Haemorrhoidal haemorrhage	10054787
Retroplacental haematoma	10054798
Hepatic haemangioma rupture	10054885
Pelvic haematoma	10054974
Pulmonary haematoma	10054991
Arteriovenous fistula site haemorrhage	10055123
Arteriovenous graft site haemorrhage	10055126
Arteriovenous fistula site haematoma	10055150
Arteriovenous graft site haematoma	10055152
Catheter site haematoma	10055662
Haemorrhagic transformation stroke	10055677
Haemorrhage	10055798
Haemorrhage coronary artery	10055803
Haemorrhage urinary tract	10055847
Postmenopausal haemorrhage	10055870
Haematoma muscle	10055890
Protein induced by vitamin K absence or antagonist II	10056243
Protein induced by vitamin K absence or antagonist II increased	10056247

PT Term	Code
Mediastinal haemorrhage	10056343
Anastomotic haemorrhage	10056346
Pituitary apoplexy	10056447
Intra-abdominal haematoma	10056457
Gastrointestinal ulcer haemorrhage	10056743
Body height decreased	10056812
Palpable purpura	10056872
Fracture debridement	10057147
Loss of proprioception	10057332
Ciliary body haemorrhage	10057417
Iris haemorrhage	10057418
Tonsillar haemorrhage	10057450
Ocular retrobulbar haemorrhage	10057571
Gastric varices haemorrhage	10057572
Fracture reduction	10057609
Cognitive disorder	10057668
Bloody discharge	10057687
Purpura non-thrombocytopenic	10057739
Peritoneal haematoma	10058095
Retroperitoneal haematoma	10058360
Spinal deformity	10058907
Thalamus haemorrhage	10058939
Putamen haemorrhage	10058940
Haemobilia	10058947
Acute haemorrhagic leukoencephalitis	10058994
Cullen's sign	10059029
Parathyroid haemorrhage	10059051
Papillary muscle haemorrhage	10059164
Intestinal haemorrhage	10059175
Haemorrhagic cyst	10059189
Adrenal haematoma	10059194
Infusion site bruising	10059203
Incision site haematoma	10059241
Intracranial haematoma	10059491
Haemorrhagic urticaria	10059499
Haemorrhagic ascites	10059766
Renal cyst haemorrhage	10059846
Anticoagulation drug level above therapeutic	10060320

PT Term	Code
Skin neoplasm bleeding	10060712
Mesenteric haemorrhage	10060717
Haematoma evacuation	10060733
Haemorrhagic ovarian cyst	10060781
Aortic rupture	10060874
Arterial haemorrhage	10060964
Cerebellar haematoma	10061038
Pelvic fracture	10061161
Genital haemorrhage	10061178
Haemorrhage foetal	10061191
Intra-abdominal haemorrhage	10061249

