Traumatic intracranial haematoma	10079013
Retinal aneurysm rupture	10079121
Bronchial varices haemorrhage	10079163
Fracture blisters	10079423
Achenbach syndrome	10079562
Metaphyseal corner fracture	10079667
Anal fissure haemorrhage	10079765
Fracture infection	10079813
Subchondral insufficiency fracture	10079864
Eye haematoma	10079891
Haemorrhagic adrenal infarction	10079902
Peripheral artery aneurysm rupture	10079908
Paranasal sinus haemorrhage	10080108
Pseudofracture	10080404
Osteophyte fracture	10080550
Gastrointestinal vascular malformation haemorrhagic	10080561
Subgaleal haemorrhage	10080900
Maisonneuve fracture	10081343
Hypophosphataemic osteomalacia	10081362
Fothergill sign positive	10081749
Growth disorder	10081945
Puncture site haematoma	10081957
Puncture site bruise	10082035
Cerebral cyst haemorrhage	10082099
Pulmonary haemorrhage neonatal	10082194
Blood loss anaemia	10082297
Pathological fracture prophylaxis	10082364
Subendocardial haemorrhage	10082459
Acquired factor IX deficiency	10082747
Extradural haematoma evacuation	10082797
Pathological tooth fracture	10082930
Pharyngeal contusion	10083176
Anticoagulant-related nephropathy	10083346
Urinary bladder haematoma	10083358
Subcapsular hepatic haematoma	10083383
Subcapsular splenic haematoma	10083384
Subcapsular renal haematoma	10083385
Oral purpura	10083533

PT Term	Code
Orbital haematoma	10083565
Spinal fracture treatment	10083586
Bullous haemorrhagic dermatosis	10083809
Pancreatic pseudocyst haemorrhage	10083813
Immune thrombocytopenia	10083842
Haemangioma rupture	10084040
Vascular anastomotic haemorrhage	10084092
Intratumoural haematoma	10084177
Antiplatelet reversal therapy	10084904
Urinary occult blood	10084960
Omental haemorrhage	10085045
Haemorrhagic occlusive retinal vasculitis	10085070
Haemorrhagic gastroenteritis	10085136
Scleral haematoma	10085163
Jugular vein haemorrhage	10085298
Gastrointestinal anastomotic haemorrhage	10085369
Heavy menstrual bleeding	10085423
Abnormal uterine bleeding	10085424
Gallbladder haematoma	10085893
Haemorrhagic cerebellar infarction	10085944
Peripheral exudative haemorrhagic chorioretinopathy	10086195
Hyper gammaglobulinaemic purpura of Waldenstrom	10086403
Intracranial haemorrhage neonatal	10086946
Hepatic artery haemorrhage	10087132

^aThe list of PTs in Appendix G was created based on MedDRA Version 25.0; as of MedDRA Version 26.0, LLT Peripheral artery haematoma has been changed from PT Peripheral artery haematoma to PT Vascular access site haematoma.

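### Appendix G, the only definition of possible sequelae of fat-soluble vitamin deficiency, omits rickets, ataxia, peripheral neuropathy and hypocalcaemia although closely related terms are listed

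*SAP*

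**What the plan says.** The revision history shows that version 2.1 of the SAP added this category and its term list. Section 9.7.1 puts it in the overall summary of TEAEs as "Any Possible Sequelae of FSV Deficiency TEAEs by SOC and PT", and Section 9.7.1.1 gives the definition: "Possible Sequelae of FSV Deficiency: based on the Specified TEAEs with PTs are listed in" Appendix G. Section 9.7.1.1 also promises a table by SOC and PT with the overall incidence, and a listing of patients. The end of Section 9.7.1 names the category among the AEs of interest that get a separate listing.

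On coding, Section 9.7.1 states: "All AEs will be classified by Primary SOC and PT according to MedDRA, Version 26.0 or higher". The footnote to Appendix G says that the list was built on MedDRA 25.0 and notes one reassignment that came with 26.0.

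**The concern.** A category defined by a closed list finds only what is on the list. In the same section, the vitamin-deficiency and diarrhoea definitions include a medical review step and hepatotoxicity uses a standardised MedDRA query. The sequelae definition has neither, so an event under an unlisted term drops out with nobody deciding that it should.

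The list also looks uneven by its own standard. It takes in osteomalacia but no rickets term. It includes loss of proprioception, diminished reflexes and disturbed gait, but not ataxia or peripheral neuropathy, the diagnoses under which an investigator might record such signs. It holds a phosphate disorder term (*Hypophosphataemia*) but not the matching calcium one. Section 9.7.1.1 says its definitions were made for the population under study, and the study title refers to children.

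At stake is the reported frequency of a safety outcome that was added on purpose. If a diagnosis is coded where the list holds only the sign, the report shows fewer patients with possible sequelae than occurred.

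**Working it through.** No formula in the plan is in question, so the check is a reading of the list and of the outputs that depend on it.

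**Step 1. Are the terms absent?** Appendix G runs in ascending code order. Its first block, down to *Xerosis*, is also nearly alphabetical, so each term has a place where it would be expected. The rest of the list was then read for any variant.

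| Concept | Neighbours at the expected place | Elsewhere in the list | Related terms that are listed |
|---|---|---|---|
| Rickets | *Rib fracture*, then *Ruptured cerebral aneurysm* | none | "Osteomalacia", "Hypophosphataemic osteomalacia", *Bone pain*, *Pseudofracture*, *Knee deformity*, *Growth retardation* |
| Ataxia | *Arterial rupture*, then *Auricular haematoma* | none | *Gait disturbance*, *Dysarthria*, *Nystagmus* |
| Peripheral neuropathy | *Neuropathic arthropathy*, then *Night blindness* | none | "Loss of proprioception", *Decreased vibratory sense*, *Areflexia*, *Hyporeflexia* |
| Hypocalcaemia | *Hyphaema*, then *Hypophosphataemia* | none | "Blood calcium decreased", *Calcium deficiency* |

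All four are absent. For hypocalcaemia there are two near-equivalents, so that gap is partial.

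**Step 2. Where would an event under an omitted term go?**

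- Left out: the sequelae line of the overall summary (9.7.1), the sequelae table and its overall incidence (9.7.1.1), and the sequelae listing (9.7.1 and 9.7.1.1).
- Still shown: TEAEs by SOC and PT, all TEAEs by descending incidence, the severity and causality tables, the serious and discontinuation tables where they apply, and the listing of all AEs.
- Not a reliable substitute: the separate vitamin-deficiency category. It is built from verbatim terms about vitamin levels or deficiency, so a report of rickets or ataxia alone need not reach it.

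**Step 3. Direction and size.** Let N be the number treated, L the number of patients with at least one listed term, and M the number with an omitted term and no listed term.

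- Incidence as planned: L/N
- Incidence with the terms added: (L + M)/N
- Difference: M/N, which is zero or positive

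The list can therefore only understate the category or leave it unchanged. A patient who also has a listed term, such as a fracture or bone pain, is already in L and does not alter the incidence. Where the summary also counts events, that patient's omitted event is still missing from the count. The SAP gives neither L nor M, so M/N cannot be calculated.

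**The case against.** The strongest reply is that the list is broad and nothing is lost from the report. It carries many bone, mineral and growth terms (*Osteopenia*, *Bone density decreased*, *Short stature*, *Growth failure*, *Spinal deformity*, *Pelvic deformity*) and many neurological ones (*Ophthalmoplegia*, *Tremor*, *Muscular weakness*). Vitamins A, E and 25-hydroxy D, INR and calcium are summarised as laboratory data, and growth is a secondary endpoint. The study does no formal hypothesis testing, and the category is descriptive.

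Most of this stands, and it limits the point. A reader might infer that the main paediatric consequences of vitamin D and E deficiency would be counted as zero. The SAP does not support that: it ranks no sequelae, and many related terms are listed. Zero capture applies only to events coded to the omitted terms.

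A reader might also infer from entries such as "Senile osteoporosis" that the list was written for adults. That does not follow either. Paediatric fracture types such as *Greenstick fracture*, *Torus fracture* and *Epiphyseal fracture* are included, and the SAP has an age group above 18 years, so adult terms are not out of place as such.

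What the reply does not answer is the category itself. A general table shows that an event of rickets occurred. It does not place the event in the group that the SAP set up to report possible sequelae. Laboratory and growth summaries are not adverse event counts.

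**Conclusion.** The point holds as a gap in a stated definition. Appendix G lacks terms for rickets, ataxia and peripheral neuropathy, and covers hypocalcaemia only in part, while including closely related terms. Followed as written, events under the omitted terms stay out of the sequelae overview line, table and listing, and the incidence of the category may be understated. Those events remain visible elsewhere in the report.

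The size is unknown. Any percentage, such as one missed patient turning 0% into 1%, would assume an event, a denominator and the absence of every listed bone term, none of which the SAP gives.

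The conclusion rests on three assumptions:

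- The text copy of Appendix G that was read is complete. A lost row cannot be fully excluded, but four separate losses would be needed.
- The omitted conditions are close enough to the listed ones to belong with them. This is a clinical judgement; the SAP gives no rationale for its selection.
- The coding dictionary holds separate preferred terms for them. This has to be confirmed in the dictionary.

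**What to change.** Before database lock, add to Appendix G the preferred terms for rickets, ataxia, peripheral neuropathy and hypocalcaemia, with names and codes taken from the MedDRA version used for coding. If any is left out on purpose, state the reason.

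At the same time, re-check the whole list against that version. The footnote deals with one change at 26.0, but Section 9.7.1 allows 26.0 or higher, and the SAP describes no check of the full list.

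The cost is a few rows in Appendix G and reruns of the overview line, the sequelae table and the sequelae listing. The reported incidence may rise slightly. If the database is already locked, the same addition can be reported as a deviation from the SAP, described and justified in the clinical study report as Section 1 requires.

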9.7.1.2 Definitions and Determination of Hepatic Events

A DSMB was formed to independently assure the safety of patients enrolled in Study A4250-008, as well as to evaluate the integrity of study conduct and the data generated. The DSMB reviews the safety data at regular, pre-defined intervals and on an ad hoc basis as needed and makes recommendations regarding patient safety and study continuance (continuation, modification, or termination of the study). The DSMB is comprised of three paediatric hepatologists and an unblinded biostatistician.

As requested by the FDA, the DSMB has been chartered to review data from patients with hepatic AEs, including cases of suspected DILI and patients with liver decompensation events as defined below. The DSMB also reviews events that are reported in the SMQ of *Drug Related Hepatic Disorders; Severe Events Only*. The DSMB reviews each case and provides their expert opinion on the aetiology of the event.

For this review, Albireo prepares slides for presentation at the DSMB meeting on each patient who meets the criteria for hepatic event adjudication. Relevant liver-related laboratory values over time and a narrative summary of relevant information is provided to the DSMB. During the open session of the meeting, an Albireo physician reviews each case with the DSMB members, responds to questions, and/or obtains any additional

information requested by the DSMB. Albireo's assessment of the hepatotoxicity aetiology is documented for each event. During the closed session, the DSMB independently assesses the event aetiology which is documented on a Hepatic Event Adjudication Form that is attached to the meeting minutes. If the DSMB requests follow-up information, this is provided at the next scheduled meeting. The Adjudication Process Document outlines the events that will be adjudicated.

